## 11.4. Determination of sample size

The sample size determination enables the evaluation of the non-inferiority of HZ recurrence incidence rate, and to rule out a 5-fold increased risk of HZ recurrence in the HZ/su group compared to the placebo group. The following assumptions were made:

- Incidence rate of HZ recurrence in the placebo group= 0.55% per year.
- Incidence rate of HZ recurrence in the HZ/su group= 0.275% per year, assuming a 50% vaccine efficacy.
- Power of 90% and Type I error of 0.025 (one-sided).
- Criterion for non-inferiority = 5-fold; the 5-fold criterion has been selected as acceptable for ruling out a moderate increased risk of HZ in a clinical trial setting.

Let  $\pi$  be the ratio of incidence rate of HZ recurrence in HZ/su group vs the placebo group, then null hypothesis  $H_0: \pi \geq 5$  vs. alternative hypothesis  $H_a: \pi < 5$ . With the assumption that the number of HZ recurrence cases in HZ/su and placebo group follows Poisson distribution independently, conditioning on the total number of cases, the number of cases in HZ/su group would follow the binomial distribution [Lehmann, 1959]. With 1:1 randomization, the parameter  $p$  in the binomial distribution (that is, the probability of HZ recurrence in HZ/su group) is expected to be  $p=\pi/(1+\pi)$ . Therefore, the above hypotheses becomes:  $H_0: p \geq 0.8333$  vs.  $H_a: p < 0.8333$ . Under the assumption of VE of 50%, a total number of 10 HZ recurrence cases is needed (PASS 12: Tests for One Proportion using proportions (Exact Test)). With incidence rate of 0.55% per year and two year follow up, 606 evaluable subjects per group are needed. Further assuming a dropout rate of 15% during the 2 year follow up period, 713 subjects per group (a total of 1426 subjects) need to be enrolled.

CCI

A large black rectangular redaction box covers the majority of the page content below the CCI label, starting from the bottom of the CCI label and extending down to just above the section 11.4.2 header.

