## 11.8. Analysis of incidence rate of Herpes Zoster recurrence

For each group, the number of subjects, person-time, number of confirmed HZ cases and incidence rate will be tabulated.

A formal non-inferiority analysis with a non-inferiority margin of 5 will be performed in the final analysis. Non-inferiority assessment will be carried out based on the fact that the distribution of two Poisson variates conditional on their sum is binomial [Lehmann, 1959]. Let  $n_1$  and  $n_0$  be the number of HZ recurrence cases,  $T_1$  and  $T_0$  (years) be total follow up, and  $r_1$  and  $r_0$  be the incidence rate in HZ/su group and placebo group respectively. It is assumed that  $n_i \sim \text{Poisson}(\lambda_i)$  ( $i=0,1$ ) and  $\lambda_i = T_i \times r_i$ , and condition on  $n = n_0 + n_1$ ,  $n_1 \sim \text{binomial}(n, p)$ , where  $p = \lambda_1 / (\lambda_1 + \lambda_0)$ . A 95% exact CI for  $p$  can be derived by using Clopper-Pearson approach, through which a 95% exact CI for  $\pi = r_1 / r_0$  (that is, the ratio of incidence rate of HZ recurrence (HZ/su versus placebo)) can be derived. Non-inferiority is met if the upper limit of the 95% CI for  $\pi$  is below 5.

In addition to performing a formal non-inferiority analysis, to further quantify the likelihood of the risk increase of HZ following Shingrix vaccination, a probability curve that the ratio of incidence of HZ recurrence (HZ/su versus placebo) is higher than  $x$ -fold ( $x$  varying from 1 to 5) will be estimated by Bayesian methodology. It will be assumed that the number of HZ cases in the HZ/su and in placebo groups follows Poisson distribution with rate (incidence rate) of  $\lambda_{HZ}$  and  $\lambda_p$  respectively. We further assume that  $\lambda_{HZ}$  and  $\lambda_p$  are random variables both with non-informative Gamma prior distribution:  $\text{Gamma}(0.001, 0.001)$ . Based on the posterior distribution of  $\lambda_{HZ}$  and  $\lambda_p$ , the probability curve of the ratio of incidence of HZ recurrence (HZ/su versus placebo), that is,  $\text{Pr}(\lambda_{HZ}/\lambda_p > x | \text{data, prior})$ , can be calculated for each given value of  $x$ . This will be further detailed in the statistical analysis plan (SAP).

The primary analysis of incidence rate of HZ recurrence will be based on the mES. The analysis will be repeated for the ES.

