5.3.1.2. Between group

A formal non-inferiority analysis with a non-inferiority margin of 5 will be performed. Non-inferiority assessment will be carried out based on the fact that the distribution of two Poisson variates conditional on their sum is binomial [Lehmann, 1959]. Let n_1 and n_0 be the number of HZ recurrence cases, T_1 and T_0 (years) be total follow up, and r_1 and r_0 be the incidence rate in HZ/su group and placebo group respectively. It is assumed that $n_i \sim \text{Poisson}(\lambda_i)$ ($i=0,1$) and $\lambda_i = T_i \times r_i$, and condition on $n = n_0 + n_1$, $n_1 \sim \text{Binomial}(n, p)$, where $p = \lambda_1 / (\lambda_1 + \lambda_0)$. A 95% exact CI for p can be derived by using Clopper-Pearson approach, through which a 95% exact CI for $\pi = r_1 / r_0$ (that is, the ratio of incidence rate of HZ recurrence (HZ/su versus placebo)) can be derived. Non-inferiority is met if the upper limit of the 95% CI for π is below 5.

In addition to performing a formal non-inferiority analysis, to further quantify the likelihood of the risk increase of HZ following *Shingrix* vaccination, a probability curve that the ratio of incidence of HZ recurrence (HZ/su versus placebo) is higher than x -fold (x varying from 1 to 5) will be estimated by Bayesian methodology. It will be assumed that the number of HZ cases in the HZ/su and in placebo groups follows Poisson distribution with rate (incidence rate) of λ_{HZ} and λ_P respectively. We further assume that λ_{HZ} and λ_P are random variables both with non-informative Gamma prior distribution: Gamma (0.001, 0.001). Based on the posterior distribution of λ_{HZ} and λ_P , the probability curve of the ratio of incidence of HZ recurrence (HZ/su versus placebo), that is, $\text{Pr}(\lambda_{HZ}/\lambda_P > x | \text{data, prior})$, can be calculated for each given value of x .

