In extreme situations, when there are no confirmed HZ cases in the HZ/su group or the Placebo group, the Gamma prior distribution will be updated to Gamma (0.015, 0.015), considering the minimum acceptable alpha in SAS is 0.015.

Considering the enrolment gap due to COVID-19, if data permit, the following sensitivity analyses will be conducted to explore between group comparisons to complement the analysis of primary endpoint:

- *A sensitivity analysis comparing HZ incidence rates between HZ/su and placebo groups on adopted mES removing the participants who received a second dose more than 2 months after the first dose (outside of the original scheduled window receiving the second dose >83 days after the first dose).*
- *A sensitivity analysis comparing HZ incidence rates between HZ/su and placebo groups stratified by enrolment pre- and post- recruitment interruption, using March 14th 2020 (the first day of site closure) as the cut-off date.*
- *Kaplan-Meier curves to compare the onset time of HZ recurrences since receipt of the first and second assigned dose.*
- *Moreover, if very different distribution between the HZ/su group and placebo group is presented, the Kaplan-Meier analysis on appropriate subintervals may also be performed.*

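### When one arm has no cases, both Gamma priors in the SAP have a shape so close to zero that the prior sets that arm's rate in the Bayesian risk curve; a minor point, visible only when cases are few

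*SAP*

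**What the plan says.** Protocol 11.8 adds a Bayesian curve to the formal non-inferiority test, in order "to further quantify the likelihood of the risk increase of HZ following Shingrix vaccination". It plots the posterior probability that the HZ/su-to-placebo rate ratio exceeds x, for x from 1 to 5. SAP 5.3.1.2 gives each arm's rate a "non-informative Gamma prior distribution: Gamma (0.001, 0.001", and SAP 5.3.2 states the Gamma posteriors and plans to simulate from them.

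For the case of no confirmed HZ in one arm, SAP 5.3.2 changes the prior: "the Gamma prior distribution will be updated to Gamma (0.015, 0.015), considering the minimum acceptable alpha in SAS is 0.015". The software limit is the only reason given. No analysis of sensitivity to the prior is planned.

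In the same situations SAP 5.3.2 sets the rate ratio to 0 if HZ/su has no cases. If placebo has none, it calls the ratio not estimable and reports each arm's rate with its interval. SAP section 6 classes the Bayesian result as descriptive.

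**The concern.** A Gamma posterior has shape equal to prior shape plus cases. With one or more cases, 0.001 or 0.015 adds almost nothing. With no cases, the prior shape is all there is, and a shape that small puts nearly all the probability at a rate of practically zero. A prior chosen to be neutral then asserts that the empty arm's true rate is close to nil.

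At stake is a published probability of increased risk. Protocol 1.3.1 lists virus reactivation in people with HZ history as a potential risk, added at the request of EU authorities, and this curve is meant to quantify it. If the placebo arm is empty, the curve is also the only numerical between-group comparison of rates that SAP 5.3.2 explicitly keeps.

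The software limit does not justify the choice of prior. It concerns simulation, and no simulation is needed: the ratio of two independent Gamma variables has an exact Beta form.

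**Working it through.** **Inputs (Protocol 11.4).** The starting figure is "Incidence rate of HZ recurrence in the placebo group= 0.55% per year". At the planned 50% efficacy the vaccine arm has half of that, 0.0055 × 0.5 = 0.00275 a year. The test is one-sided at 0.025 with 90% power, and the margin is a rate ratio of 5. Also 606 evaluable per group, two years of follow-up and 15% dropout.

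**The plan's own figures reproduce.** Under the null p = 5/6; under 50% efficacy p = 0.5/1.5 = 1/3. In the exact binomial test at one-sided 0.025, 9 cases give power 0.855. With 10 cases the test rejects at 5 or fewer in HZ/su, with actual error 0.0155 and power 0.923. This matches "a total number of 10 HZ recurrence cases is needed". Subjects per group: 10 / [2 × (0.0055 + 0.00275)] = 606; 606 / 0.85 = 713.

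**Person-time (equal arms assumed).** 606 × 2 = 1,212 person-years per arm. As an upper bound, if everyone were followed for the roughly 4-year maximum in Protocol 5.3, 606 × 4 = 2,424.

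**Chance of an empty arm.** P(0) = exp(−person-years × rate). The expected placebo count is 1,212 × 0.0055 = 6.67.

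| Arm and efficacy | 1,212 PY | 2,424 PY |
|---|---|---|
| HZ/su, 50% (planned) | exp(−3.33) = 3.6% | 0.1% |
| HZ/su, 89.8% (pivotal) | exp(−0.68) = 51% | 26% |
| HZ/su, 97.2% (pivotal) | exp(−0.187) = 83% | 69% |
| Placebo | exp(−6.67) = 0.13% | below 0.001% |

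At 1,212 person-years, the chance of at most three placebo cases is 0.00127 × (1 + 6.67 + 22.2 + 49.4) = 10%.

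**Upper limit for the rate in an empty arm.** The posterior is Gamma(a + 0, b + 1,212). Its 97.5% point per 1,000 person-years is about 0 for Gamma(0.001, 0.001), 0.10 for Gamma(0.015, 0.015), 2.07 for Jeffreys Gamma(0.5, rate near 0) and 3.04 for Gamma(1, rate near 0). The exact Poisson limit from SAP 9.2.1 is −ln(0.025)/1,212 = 3.04 per 1,000.

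**The curve.** With n1 HZ/su and n0 placebo cases,

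Pr(ratio > x) = Pr{Beta(a + n1, a + n0) > x(b + T1) / [x(b + T1) + b + T0]}.

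With equal person-time the cut-point is x/(1 + x), that is 1/2 at x = 1 and 5/6 at x = 5. A hand check with Gamma(1, near 0): 0 against 2 gives (1/2)³ = 0.125, and 1 against 0 gives 1 − (5/6)² = 0.306.

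| HZ/su v placebo cases | Quantity | 0.001 | 0.015 | Jeffreys | Gamma(1) |
|---|---|---|---|---|---|
| 0 v 7 | Pr(ratio > 1) | 0.000002 | 0.00003 | 0.0015 | 0.0039 |
| 0 v 3 | Pr(ratio > 1) | 0.00007 | 0.001 | 0.033 | 0.0625 |
| 0 v 2 | Pr(ratio > 1) | 0.0002 | 0.003 | 0.076 | 0.125 |
| 1 v 0 | Pr(ratio > 5) | 0.998 | 0.974 | 0.505 | 0.306 |
| 3 v 0 | Pr(ratio > 5) | 0.999 | 0.991 | 0.725 | 0.518 |
| 3 v 7 | Pr(ratio > 1) | 0.090 | 0.090 | 0.102 | 0.113 |

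The 0.001 column is shown for comparison; in the zero-case rows the SAP would use 0.015.

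**Against the plan's exact interval (SAP 5.3.1.2).**
- 0 v 2: the upper limit for p is 1 − √0.025 = 0.842, so the ratio limit is 0.842/0.158 = 5.3, which fails the margin of 5. The curve would show 0.003 for any increase at all.
- 1 v 0: the lower limit is 0.025/0.975 = 0.026, so the data do not exclude a large benefit. The curve would show 0.974 for more than a five-fold increase.
- 0 v 7: the upper limit is 0.69, and the curve and the interval agree.

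**The case against.** Several stronger readings are tempting, and the documents do not support them.

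- **The switch to 0.015 causes the trouble.** It does not. In an empty arm 0.015 is less extreme than the default, as every zero-case row of the table shows. Deleting the switch and keeping 0.001 would make matters worse.
- **The switch is an after-the-fact choice.** It depends on the data, but the rule is written into the SAP, and there is one final analysis with no interim.
- **The protocol's efficacy figures make the situation likely.** The 51% to 83% needs efficacy of 89.8% to 97.2% to carry over. Protocol 1.2.1 says that most earlier HZ/su studies in older adults excluded people with HZ history, and this trial plans on 50%, which gives 3.6%.
- **The curve would mislead in the usual zero-case result.** With about the expected number of placebo cases it would not. For 0 v 7 the gap from Jeffreys is about 0.15 percentage points at x = 1 and nil at x = 5. The ratio of the two probabilities is large only because both are tiny.
- **The conclusion on non-inferiority could change.** It cannot: it rests on the exact conditional interval against 5.

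It can also be said that with one case in total every prior drives the answer, since Jeffreys gives 0.505 and Gamma(1) gives 0.306 for 1 v 0. That stands, and it is a reason to display more than one prior.

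**Conclusion.** The point holds as a minor one. In an arm with no cases, both the default and the substitute prior fix that arm's rate near zero, with a 97.5% limit at most about one thirtieth of the exact Poisson limit (0.10 against 3.04 per 1,000 person-years).

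The effect on the curve depends on the other arm. It is negligible at about 7 placebo cases and visible at 2 or 3. It is large with no placebo cases, which has probability 0.13% under the plan's rates. The joint chance of no HZ/su cases and at most three placebo cases is about 0.036 × 0.10 = 0.4% at the planned efficacy. It is 5% to 8% (0.51 × 0.10 to 0.83 × 0.10) if the pivotal efficacies applied.

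These figures assume Poisson counts, equal person-time, 1,212 person-years per arm and a placebo rate of 0.55% per year. Longer follow-up makes empty arms rarer. Jeffreys and Gamma(1) serve as comparators, not as the truth.

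**What to change.** In SAP 5.3.1.2 and 5.3.2:

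1. Pre-specify one prior for all outcomes with a shape not near zero, for example Jeffreys, Gamma(0.5, rate near 0).
2. Delete the zero-case substitution. Do this only together with step 1.
3. Compute Pr(ratio > x) exactly from the Beta formula above in place of simulation.
4. Show the curve under at least one alternative, for example Gamma(1, rate near 0), so that dependence on the prior can be seen.

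The cost is a few lines of SAP text and simpler code. The curve becomes slightly less favourable if HZ/su has no cases. Nothing changes in the primary analysis or the sample size.

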5.4. Immunogenicity

5.4.1. Analysis of immunogenicity planned in the protocol

The primary analysis will be based on the PPS for analysis of immunogenicity. If, in any group, the percentage of vaccinated subjects with serological results excluded from the PPS for analysis of immunogenicity is 5% or more, a second analysis based on the ES will be performed to complement the PPS analysis.

5.4.1.1. Humoral immune response

[figure not shown]
5.4.1.1.1. Within group assessment

The following descriptive analyses will be performed for each group and by age stratum (50-59 YOA; 60-69 YOA and \geq 70 YOA) and by 'time since previous HZ episode' (\leq 4 years ago, 5-9 years ago, \geq 10 years ago):

- Seropositivity rate at Day 1, Month 2 and Month 3 with exact 95% CI
- GMC at Day 1, Month 2 and Month 3 with 95% CI
- VRR (vaccine response rate) at Month 2 and Month 3 with exact 95% CI.

Descriptive statistics of the fold increase over pre-vaccination for anti-gE antibody concentration at Month 2 and Month 3 (Mean, SD, Min, Q1, Median, Q3, Max).

CCI

A large rectangular area of the page is completely blacked out, indicating that the content has been redacted. The only text visible in this area is the label 'CCI' in the top-left corner.

5.4.2. Additional considerations

None

5.5. Analysis of safety and reactogenicity

5.5.1. Analysis of safety and reactogenicity planned in the protocol

[figure not shown]
The analysis will be performed on the ES. When appropriate, tabulations will be presented overall and by time of occurrence relative to last vaccination (e.g., using windows such as Days 1-7, Days 1-30 and more than 30 days post-vaccination). Safety analyses will also be performed by age stratum (50-59 YOA; 60-69 YOA and \geq 70 YOA) and by 'time since previous HZ episode' (\leq 4 years ago, 5-9 years ago, \geq 10 years ago).

The results for the analysis of safety will be tabulated as:

- The proportion of subjects with at least one local AE (solicited or unsolicited), with at least one general AE (solicited or unsolicited) and with any AE (solicited or unsolicited) during the 7-day follow-up period will be tabulated with exact 95% CI after each vaccine dose and overall.

- The proportion of subjects with at least one local AE (solicited only), with at least one general AE (solicited only) and with any AE (solicited only) during the solicited 7-day follow-up period will be tabulated with exact 95% CI after each vaccine dose and overall.
- The proportion of subjects reporting each individual solicited local and general AE during the solicited 7-day-follow-up period will be tabulated with exact 95% CI.
- For all solicited AEs, the same tabulation will be performed for grade 3 solicited AEs and for solicited general AEs with relationship to vaccination
- The proportion of solicited AEs resulting in a medically attended visit will be tabulated.
- Total duration of each individual solicited local and general AE will be tabulated.
- The proportion of subjects reporting temperature by half degree (°C) cumulative increments. Similar tabulations will be performed for any fever with a causal relationship to vaccination and for any fever resulting in a medically attended visit.
- The proportion of subjects with at least one report of unsolicited AE classified by the MedDRA system organ class (SOC) and preferred term (PT) and reported up to 30 days after each vaccination will be tabulated with exact 95% CI.
- The same tabulation will be performed for grade 3 unsolicited AEs (including serious AE) and for unsolicited AEs with a relationship to vaccination. The proportion of AEs resulting in a medically attended visit will also be tabulated.
- Total number/percentages of doses (per dose and overall) followed by AEs will be tabulated.
- All pIMDs and related pIMDs occurring from first vaccination up to 30 days post last vaccination will be tabulated.
- All pIMDs and related pIMDs occurring after 30 days post last vaccination until 1 year post last vaccination will be tabulated.
- All SAEs, related SAEs occurring from first vaccination up to 30 days post last vaccination will be tabulated.
- All SAEs, related SAEs occurring after 30 days post last vaccination until one year post last vaccination will be tabulated.
- Fatal SAEs will be tabulated using date of onset of SAE in the following manner – within Day 1-Month 3 (30 days post last vaccination), Day 1 to Month 14 (one year post last vaccination) and during the entire study period. Fatal SAEs will also be tabulated using the date of death within the same time periods.
- All SAE related to investigational vaccine, related to study participation or to GSK concomitant medication/vaccine occurring during the entire study period will be tabulated.
- AEs/SAEs leading to withdrawal from the study will be tabulated.

CCI

- [REDACTED]
- [REDACTED]
- [REDACTED]

CCI

5.5.2. Additional considerations

Following additional tables will be generated:

- Number and percentage of subjects with at least one report of a grade 3 non-serious unsolicited AE during the 30-day (Days 1–30) follow-up period after each vaccination classified according to the MedDRA SOC and PT will be tabulated, with exact 95% CI. The same will be generated for grade 3 non-serious unsolicited AE considered related to vaccination.
- Listing of subjects with fatal SAE during the entire study period including the associated events will be generated on Enrolled Set.
- Listing of all SAEs up to end of study will be generated on Exposed Set.
- Listing of subjects with a suspected HZ episode, PCR final result and HZAC final result from first administered dose up to end of study will be generated on Exposed Set.
- Listing of (S)AEs and solicited adverse events leading to study or treatment discontinuation up to end of study will be generated on Exposed Set.
- Duration of each individual solicited local and general AE within the solicited follow-up period will be tabulated.
- ***COVID-19 infection cases identified during the study will be assessed as follows:***
 - ***Numbers and percentage of subjects with a suspected, probable or confirmed COVID-19 infection will be summarized by group based on ES.***
 - ***Number and percentage of subjects who had a COVID-19 infection reported as an AE or SAE will be summarized by group on ES.***
- ***Number and percentage of subjects who had a COVID-19 infection leading to study or treatment discontinuation be summarized by group on ES.***

6. ANALYSIS INTERPRETATION

The primary objective of non-inferiority of the incidence of HZ recurrence in the HZ/su and placebo groups is considered met if the upper limit of the 95% CI of the ratio of the incidence of HZ recurrence (HZ/su versus placebo) is below 5.

For all secondary objectives, analyses will be descriptive with the aim to characterize the differences in reactogenicity, safety and immunogenicity between groups.

The ratio of incidence of HZ recurrence (HZ/su versus Placebo) calculated using Bayesian methodology will be a descriptive analysis to provide additional information about incidence rate ratio between Hz/su and Placebo based on simulated data with assumption provided (sections [5.3.1.2](#) and [5.3.2](#)) of the SAP.

7. CONDUCT OF ANALYSES

Any deviation(s) or change(s) from the original statistical plan outlined in the study protocol will be described and justified in the final clinical study report (CSR).

7.1. Sequence of analyses

There will be only one final analysis at the end of the study.

A CSR containing all data will be written and made available to the investigators.

If the data for tertiary endpoints become available at a later stage, (an) additional analysis/ analyses will be performed. These data will be documented in annex(es) to the study report.

Description	Disclosure Purpose (CTRS=public posting, SR=study report, internal)
Final analysis	CTRS, SR

7.2. Statistical considerations for interim analyses

No interim analyses are planned.

8. CHANGES FROM PLANNED ANALYSES

Following are the changes from the planned analysis described in the protocol:

- Two new cohorts – Enrolled Set and Randomized Set have been defined as required for web disclosure and SAE tables presentation on Enrolled Set.
- The PPS population has been defined separately for the humoral immune response and [CCI](#) for each timepoint.
- Evaluation of duration of unsolicited adverse event has been removed from endpoint as it is mistakenly added.
- The grading of fever (grade 1 and grade 2) has been changed from protocol to align with other studies in Zoster project. Refer to section [9.1.4](#) for grading of fever.
- Timeframe of fatal SAE reporting from Month 3 to study end is changed to Day 1 to study end.
- The definition of modified Exposed Set has been modified to exclude the subjects who has not received vaccination per protocol.

- *For the primary endpoint, added a sensitivity analysis on mES after removing the participants who received a second dose more than 2 months after the first dose (outside of the original scheduled window), added a stratified analysis by recruitment interruption, and Kaplan-Meier curves to compare the onset time of HZ recurrences if applicable.*
- *Added analysis to assess the impact of COVID-19 on safety.*

